6.5.8 Complications of Prematurity

The incidence of IVH, PVL, PDA, NEC, apnea, pulmonary hemorrhage, acquired sepsis, and air leak will be summarized by treatment group. The worst grade of IVH and the worst stage of NEC will also be summarized by treatment group. In addition, the incidence and stage of ROP will be summarized by treatment group.

7 INTERIM ANALYSES AND DATA MONITORING

7.1 SAFETY REVIEW COMMITTEE

Safety is to be monitored by a Safety Review Committee (SRC), also known as a Data Monitoring Committee (DMC). Data analyses will be performed by an independent statistician who is a non-voting member of the SRC. As this is an open-label study, the reports from each interim analysis will be unblinded. The interim analyses are for assessing safety, trial conduct and ethical issues.

7.2 INTERIM ANALYSES

Four interim analyses are planned. Each interim analysis will occur when all subjects from each dosing group have been enrolled and all active subjects have completed 72 hours. In addition to the planned analyses, if more than 2 subjects in any dosing group experience an SAE related to dosing, aerosol delivery will be suspended and further dosing will proceed only if and when the SRC deems it to be appropriate.

In addition, if a treated subject dies due to a related event during or within 12 hours after aerosol administration, then an unscheduled meeting of the SRC will be called. Safety and tolerability data will be presented to the SRC for their immediate review. Study enrollment will be suspended until such time that a safety assessment has been completed and dosing will proceed only if and when the SRC deems it to be appropriate. If the SRC deems it to be appropriate to re-initiate enrollment after an enrollment hold, local IRB approvals will be obtained before the re-initiation of subject screening and enrollment activities. The objective of the interim analyses is to ensure the safety of subjects at a particular dose before proceeding to the next higher dose.

7.3 DATA MONITORING

A system of computerized data validation checks will be implemented and applied to the study database on a regular basis. Queries will be entered, tracked, and resolved through the electronic data capture (EDC) system directly. The study database will be updated in accordance with the resolved queries. All changes to the study database will be documented.

A detailed data surveillance plan (DSP) will be produced by the Department of Biometrics. The data surveillance plan (DSP) describes statistical surveillance methods and presentations used to check and evaluate the study conduct and data quality. This is designed to detect anomalous data, data entry errors in the summary outputs, and ensure the quality of the collected data through the use of frequency, trending and other statistical techniques.

Data surveillance activities on frequency monitoring should include, but are not limited to: data anomalies (eg, outliers, potential protocol violators), data entry errors (missing data values, inconsistent data values), criteria violations, and the number of subjects experiencing early termination from the study. Data surveillance activities on trend review include, but are not limited to: the evaluation, documentation, presentation and reporting of (1) recorded endpoint variables, (2) AEs and SAEs, (3) unanticipated adverse device effects (UADEs), and (4) subject deaths.

The DSP will be produced and updated periodically with the periods defined by the Department of Biometrics. Data surveillance procedures described in the plan will take place at least quarterly, depending upon the rate of subject enrollment and the timing of study closure activities.

8 STATISTICAL TECHNICAL ISSUES

8.1 METHODS OF ASSIGNING SUBJECTS TO TREATMENT GROUPS

An overall randomization list will be prepared by Discovery's Biometrics department such that subjects will be randomly assigned to lucinactant or control (nCPAP alone). Each subject's random assignment will be provided to an interactive web response system (IWRS). As soon as possible after a subject meets the entry criteria and is eligible to be enrolled, the PI or authorized designee will log in to the IWRS and complete the randomization procedures. Subjects that discontinue the study prematurely will not be replaced.

8.2 BLINDING/MASKING

This study is open label; thus, no blinding or masking procedures are employed.

8.3 DETAILS ON STATISTICAL METHODS

Not applicable for this study.

8.4 MULTIPLICITY

Since the primary purpose of this study is safety and tolerability, and since no statistical testing will be performed, no adjustment for multiplicity will be done.

8.5 SAMPLE SIZE RE-ESTIMATION

Sample size re-estimation will not be used in this study.

9 GENERAL ANALYSIS DEFINITIONS

All summaries and statistical analyses will be generated using SAS[®] System for Windows[™], version 9.1 or higher.

9.1 BASELINE DEFINITION

Baseline is defined as the last measurement prior to study drug administration for subjects randomized to the active group, and randomization for subjects randomized to the control group.

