7.1.1 Vital Signs

Baseline vital signs (body temperature, respiratory rate, and heart rate) will be documented within 15 minutes (± 5 minutes) before randomization and at the following time points from the time of randomization: 1, 3 (± 15 minutes), 6, 12 (± 1 hour), 18, 24, 36, and 48 hours (± 2 hours) post-randomization.

Subjects randomized to the active study arm will have additional vital signs (respiratory rate and heart rate) documented every 5 minutes (± 2 minutes) during the administration of lucinactant for inhalation for Dosing Group I and II. For Dosing Groups III and IV, vital signs will be documented every 15 minutes (± 5 minutes) after randomization.

For all dosing groups, subjects randomized to the nCPAP only arm will have additional vital signs (respiratory rate and heart rate) documented 15 minutes (± 5 minutes) after randomization.

For all randomized subjects, daily vital sign assessments (body temperature, respiratory rate, and heart rate) must be performed at 0800 hours (\pm 2 hours) from Study Day 3 to the completion of Study Day 7.

Sustained heart rate $<$ 100 bpm for \geq 20 seconds must be noted as an AE of bradycardia in the study eCRF.

In this study, a sustained apnea event is defined as lasting \geq 20 seconds and is coincident with at least one of the following: (1) HR $<$ 100 bpm, (2) desaturation (oxygen saturation $<$ 80%), (3) requirement for intermittent positive pressure breaths using inflating pressures above the set CPAP pressure administered manually or mechanically through any patient interface.

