7.1.3 Pulse Oximetry

SpO₂ will be monitored continuously from the time of randomization until completion of Study Day 7.

Sustained SpO₂ $<$ 80% for \geq 20 seconds must be recorded as an AE in the study eCRF.

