7.1.4 FiO₂

FiO₂ values will be recorded at different times throughout the study. At a minimum, FiO₂ values are: 1) recorded at specified time points while a subject is receiving nCPAP, 2) recorded every 12 hours when a subject is receiving other types of respiratory support or supplemental oxygen, 3) recorded every 15 minutes for 3 hours after randomization, and 4) recorded every 6 hours from randomization through 72 hours.

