7.1.5 Monitoring of Carbon Dioxide Levels

PCO₂ measurements for subjects in both the active and control groups will be resulted through the use of continuous transcutaneous monitor.

PCO₂ monitoring must be initiated following randomization (for subjects randomized to the active study arm, monitoring must be initiated at least 30 minutes before the start of ADS

delivery) and continue for 72 hours post randomization. The transcutaneous monitor must be calibrated for accuracy against blood gas values (arterial, capillary or venous) at the time of initial set-up, and recalibrated as necessary in accordance with local institutional practices to ensure accuracy of the monitor output.

In the eCRF, PCO₂ values will be recorded every 15 minutes through 3 hours after randomization, and every 6 hours from randomization through 72 hours.

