Appendix 2 Protocol Event Schedule Summarization

Measurement/Procedure	Study Period			
	Screening	Primary Observation	Extended Observation	Final Observation
		Days 1-2	Days 3-7	Day 8 to 36w PMA Final Visit (36w PMA)
Informed Consent/HIPAA	X			
Inclusion/Exclusion Criteria	X			
Demographics	X			
Maternal/Birth History ¹	X			
Physical Exam	X			X
Chest Radiograph ²	X			
Randomization		X		
Lucinactant for inhalation		X		
Body Weight		X ¹		
Defecation ³		X		
Vital Signs		X ⁴	X ⁴	
Monitoring of SpO ₂ ⁵		X	X	
Monitoring of PCO ₂ ⁶		X		
Respiratory support and O ₂ delivery	X	X	X	X ⁷ X ⁷
Serum Electrolytes		X ⁸		
Gastric Liquid Volume ⁹		X		
Peri-Dosing Events ¹⁰		X		
Adverse Events		X	X	X X
Adverse device effects		X		
Concomitant Medication		X	X	X X

Note: Day 1 for all subjects is the day of study randomization.

¹ Birth weight will be captured with birth history and as the first body weight obtained after randomization (Section 7.1.2).

² A chest radiograph prior to intubation (refer to Sections 7.1.8, 7.5), is required if such a procedure does not delay or compromise the emergent care of the subject.

³ The number of stools occurring within 24 hours from the time of randomization is to be recorded (Section 7.1.10).

⁴ Vital signs will be documented within 15 minutes (± 5 minutes) prior to randomization. For the active arms, vital signs will be documented every 5 minutes (± 2 minutes) during dosing for Dosing Group I and II; every 15 minutes (± 5 minutes) during dosing for Dosing Group III and IV. For the control arms, vital signs will be documented at 15 minutes (± 5 minutes) post randomization (Section 7.1.1). In addition, record at 1, 3 (± 15 minutes), 6, 12 (± 1 hour), 18, 24, 36 and 48 hours (± 2 hours) post randomization and daily at 0800 (± 2 hours) on days 3 to 7 for all randomized subjects.

⁵ Continuous monitoring of oxygen saturations by pulse oximetry will be initiated at the time of randomization and continued until completion of Study Day 7 (Section 7.1.3).

⁶ Continuous trancutaneous PCO₂ monitoring is to be initiated following randomization and at least 30 minutes prior to the start of ADS delivery, and continued for 72 hours post randomization (Section 7.1.5).

⁷ Only the date and time of the initiation and discontinuation of ventilator and pressure support is to be documented in the study eCRF from Study Day 8 to Final Study Visit (Section 7.6).

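### SAP 9.1 sets baseline before dosing in active infants but at randomisation in controls, so early tabulated changes from baseline cover different intervals in the two arms

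*SAP*

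**What the plan says.** **Baseline.** SAP 9.1: "Baseline is defined as the last measurement prior to study drug administration for subjects randomized to the active group, and randomization for subjects" in the control group. Protocol 7.1.1 uses the same word for a pre-randomisation value in all infants: "Baseline vital signs (body temperature, respiratory rate, and heart rate) will be documented within 15 minutes", with a tolerance of 5 minutes, before randomisation.

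**Clock.** Protocol 7.1.4 has FiO2 "recorded every 15 minutes for 3 hours after randomization", then every 6 hours through 72 hours. Protocol 7.1.5 sets the same recording times for PCO2. Routine vital signs fall at 1, 3, 6, 12, 18, 24, 36 and 48 hours from randomisation. SAP 9.2 has summary tables use scheduled rather than actual times.

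**Start of dosing.** Protocol 2.1 and 5.2.1 require aerosol to start within 2 hours of randomisation. Protocol 7.1.5 says of PCO2 that "monitoring must be initiated following randomization", and that in the active arm "monitoring must be initiated at least 30 minutes before the start of ADS" delivery.

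**SpO2.** Protocol 7.1.3 says it "will be monitored continuously from the time of randomization until completion of Study Day 7", without recording times.

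**Outputs.** SAP 6.5.6 calls for observed values and change from baseline for FiO2, PCO2 and SpO2 over 72 hours, with figures. Tables 7.1.1 to 7.1.3 do the same for vital signs. Figures 2.1 to 2.3 show change from baseline for all active infants and controls.

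**The concern.** A change score is comparable between arms only if it runs over the same interval. Here the control interval starts at randomisation and the active interval starts just before dosing, yet both are read at the same nominal time after randomisation. Two things follow.

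- The active change covers less time than the control change, by an amount that depends on how quickly dosing began.
- Some active readings come before the baseline they are compared with. The SAP has no rule for them.

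Vital signs give a simple example. If dosing starts after the 1 h reading, and that reading is the last pre-dose temperature, its change from baseline is zero by construction. The protocol's own pre-randomisation baseline is set aside for that infant.

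The displays matter because Protocol 3.2 asks whether physiological parameters can feasibly serve as a measure of improvement, compared with nCPAP alone. With no modelling planned, the tables and figures are the result, and the mismatch is largest in the first hours, where an acute response would be sought.

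**Working it through.** The plan states no figure on this point, so there is none to reproduce. The check is timing arithmetic.

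**Inputs**
- Reading times g = 15, 30, ..., 180 min from randomisation: 12 readings (Protocol 7.1.4 and 7.1.5).
- Later readings every 6 h to 72 h (same sections).
- Dose start s between about 30 min (the PCO2 lead time in 7.1.5) and 120 min (Protocol 2.1).
- Control baseline at 0 min, assuming a value exists at randomisation.

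The documents give no distribution of s, so only the range is shown.

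**Formulas**
- Active baseline reading b is the last scheduled reading before dosing. If a reading at the start minute counts as pre-dose, b = max g ≤ s (inclusive). If it must be earlier, b = max g < s (strict).
- Readings before baseline = number of g < b.
- Interval covered at nominal time t = t − b in active infants, and t in controls.

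**Results (inclusive / strict)**

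| s (min) | b (min) | Readings before b, of 12 | 180 − b (min) | 360 − b (min) | (4320 − b)/60 (h) |
|---|---|---|---|---|---|
| 30 | 30 / 15 | 1 / 0 | 150 / 165 | 330 / 345 | 71.5 / 71.75 |
| 60 | 60 / 45 | 3 / 2 | 120 / 135 | 300 / 315 | 71 / 71.25 |
| 90 | 90 / 75 | 5 / 4 | 90 / 105 | 270 / 285 | 70.5 / 70.75 |
| 120 | 120 / 105 | 7 / 6 | 60 / 75 | 240 / 255 | 70 / 70.25 |
| Control | 0 | – | 180 | 360 | 72 |

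The two rules differ only when dosing starts exactly on a 15-minute mark. Starts at 40, 70 and 100 min give b = 30, 60 and 90, and counts of 1, 3 and 5, under both.

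**Active interval as a share of the control interval**
- 3 h: 60/180 = 33% to 165/180 = 92%.
- 6 h: 240/360 = 67% to 345/360 = 96%.
- 72 h: 70/72 = 97% to 71.75/72 = 99.7%.

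**How far this carries to each parameter**
- *FiO2.* The counts apply as shown if baseline is a scheduled reading.
- *PCO2.* The counts are maxima. If the 15-minute grid binds from the start, they match FiO2. If monitoring begins only 30 min before a dose at 120 min, the available pre-dose readings are 90, 105 and 120 min. Then 2 precede baseline (inclusive) or 1 (strict), not 7 or 6. The control baseline is also uncertain: a first reading at 15 min would make the control 3 h interval 180 − 15 = 165 min.
- *SpO2.* No count is possible without recording times.
- *All parameters.* Protocol 2.3.1 mentions a pre-treatment assessment without defining its content. If it supplies an off-grid pre-dose value, b moves and these figures change, including the 1 h vital-sign example.

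**The case against.** The strongest reply is that nothing is tested or modelled, so a baseline convention in a descriptive table can do little harm. Adverse events do not use a baseline. The enrolment-hold criteria rest on related serious adverse events and early related deaths. Observed values are shown alongside the changes. All of this stands and limits the point to how the early change displays are read.

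A second reply is that a last pre-dose baseline is conventional and isolates the drug, while controls have no dose to anchor on. That is a good reason to keep it for an active-arm display. It does not justify placing it beside a randomisation baseline on a randomisation clock.

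Third, the figures may be unaffected. SAP 9.2 speaks of summary tables. The rule that times run from randomisation is in SAP 4.3, under efficacy, and allows exceptions, whereas the respiratory displays are in SAP 6.5.6, under safety. This also stands: the mismatch reaches Figures 2.1 to 2.3 only if they use the randomisation clock, which the SAP does not state.

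A reader might go further and infer that the changes are biased for or against lucinactant, or that the safety conclusions are compromised. The documents do not support either. The direction depends on how FiO2, PCO2 and vital signs move between randomisation and dosing, which is not given.

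**Conclusion.** The point holds for the tabulated changes from baseline, and conditionally for the figures. At nominal 3 h the active interval is about 60 to 165 min against 180 in controls. At 6 h it is about 240 to 345 against 360. By 72 h the difference is negligible. Up to 7 of 12 early FiO2 readings can precede their own baseline; for PCO2 that is an upper limit.

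These figures assume dosing starts 30 to 120 min after randomisation, baseline is a scheduled reading, and controls have a value at randomisation. It would be wrong to take 7 of 12 as typical: it needs a start at 2 h and a reading at the start minute counted as pre-dose.

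The consequence is confined to descriptive displays, but the correction is cheap and should be made before database lock.

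A separate point should not be counted towards this one. Protocol 7.1.1 says "For Dosing Groups III and IV, vital signs will be documented every 15 minutes" after randomisation, whereas Appendix 2 and the SAP schedule say "during dosing for Dosing Group III and IV". Those passages must be reconciled.

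**What to change.** Amend SAP 9.1 and 6.5.6, and apply the change to Tables 7.1.1 to 7.1.3 and 7.5.1 to 7.5.3 and to the change-from-baseline figures.

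1. **Between-arm displays: one randomisation-anchored baseline in both arms.**
   - Vital signs: the pre-randomisation value.
   - FiO2: the value documented with the nCPAP settings at randomisation. Protocol 5.4.1.3 requires those settings then, and 5.4.1.1 lists FiO2 among them. Protocol 8.2 and SAP 6.2 list FiO2 separately, so confirm on the eCRF that it is captured at that time. If not, use the first post-randomisation reading before any dosing, by the same rule in both arms.
   - PCO2: the first valid reading after monitor set-up, before dosing if active. State that this is only approximately at randomisation, and report its time by arm. Unequal set-up times would be disclosed, not removed.
   - State the SpO2 times used and the time axis of the figures.
2. **Active-arm-only display.** Keep the last pre-dose value as baseline and plot by actual time from the start of aerosol. State whether a reading at the start minute counts as pre-dose.

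**Downside.** The randomisation baseline includes up to 2 h of pre-dose change in active infants, and the second display has no control comparator.

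**Cost.** SAP wording and a little more programming. Pre-randomisation vital signs, nCPAP settings at randomisation, aerosol start and end times, and clock times are already to be recorded. Subject to the eCRF check, this fix needs no protocol amendment and does not depend on resolving the Group III and IV timing conflict.

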9.2 WINDOWS FOR VISITS

Accurate clock times will be recorded for each timed event in military time (24-hour clock). Day 1 is the day on which randomization occurs; Day 3 begins at midnight 2 days following randomization and Day 7 will be the sixth day after the day of randomization.

All assessments at pre-specified time points are to be conducted within the windows specified in the protocol. Summary tables will use the pre-specified time points, not the actual times, to summarize the data.

9.3 SITE POOLING METHODS

As no statistical modeling will be performed, pooling of centers will not be done.

11 LIST OF TABLES

Table	Title
1.1	Subject Disposition – Study Populations – All Subjects
1.2	Subject Disposition – Study Completion/Termination Status – All Subjects
1.3	Subject Disposition – Protocol Deviations/Violations – All Subjects
2.1	Subject Demographics – Intent-to-Treat Population
2.2	Medical Information – Maternal History – Intent-to-Treat Population
2.3	Medical Information – Birth History – Intent-to-Treat Population
3.1	Concomitant Medications – Safety Population
3.2	Number of Treatments Received – Safety Population
4.1.1	Exploratory Efficacy Analysis – Early Worsening of Respiratory Status Criteria – Intent-to-Treat Population
4.1.2	Exploratory Efficacy Analysis – Late Worsening of Respiratory Status Criteria – Intent-to-Treat Population
4.2	Exploratory Efficacy Analysis – BPD and Survival Without BPD at 36 Weeks PMA – Intent-to-Treat Population
4.3	Exploratory Efficacy Analysis – Time until Intubation for Mechanical Ventilation – Intent-to-Treat Population
4.4	Exploratory Efficacy Analysis – Time until Any Intubation – Intent-to-Treat Population
5.1	Investigational Device – Technical Performance – Safety Population
5.2	Investigational Device – Early Termination of Treatment – Safety Population
6.1	Peri-Dosing Adverse Events – Safety Population
6.2	Air Leak – Safety Population
6.3.1	Treatment-Emergent Adverse Events by System Organ Class and Preferred Term – Safety Population
6.3.2	Treatment-Emergent Adverse Events by System Organ Class, Preferred Term, and Severity – Safety Population
6.3.3	Treatment-Emergent Adverse Events by System Organ Class, Preferred Term, and Relationship – Safety Population
6.3.4	Treatment-Emergent Adverse Events by Severity and Relationship to Study Drug – Safety Population
6.3.5	Treatment-Emergent Adverse Events in Descending Order by Total Active Group – Safety Population
6.4.1	Serious Adverse Events by Preferred Term Displayed in Descending Order by Total Active Group – Safety Population
6.5.1	Adverse Device Effects by Treatment Group – Safety Population
6.6	All-Cause Mortality – Safety Population

- 7.1.1 Clinical Assessments – Vital Signs – Body Temperature – Observed Values and Change from Baseline – Safety Population
- 7.1.2 Clinical Assessments – Vital Signs – Respiration Rate – Observed Values and Change from Baseline – Safety Population
- 7.1.3 Clinical Assessments – Vital Signs – Heart Rate – Observed Values and Change from Baseline – Safety Population
- 7.2 Clinical Assessments – Serum Electrolytes – Observed Values – Safety Population
- 7.3 Clinical Assessments – Gastric Liquid Volume and Defecation – Safety Population
- 7.4.1 Clinical Assessments – Physical Examination – Safety Population
- 7.4.2 Clinical Assessments – Physical Examination: Shift Table – Safety Population
- 7.5.1 Clinical Assessments – Respiratory Parameters – FiO₂ – Safety Population
- 7.5.2 Clinical Assessments – Respiratory Parameters – SpO₂ – Safety Population
- 7.5.3 Clinical Assessments – Respiratory Parameters – PCO₂ – Safety Population
- 7.6.1 Clinical Assessments – Respiratory Support in the Delivery Room and Mechanical Ventilation – Safety Population
- 7.6.2 Clinical Assessments – Supplemental Oxygen – Safety Population
- 7.7 Clinical Assessments – nCPAP Settings – Safety Population
- 7.8 Clinical Assessments – Complications of Prematurity – Safety Population

Listing Title

- 1.1 Protocol Violations/Deviations
- 2.1 All-Cause Mortality
- 2.2 Serious Adverse Events
- 3.1 Early Termination of Aerosol Treatment
- 3.1 Pre-Study/Concomitant Medications
- 4.1 Mechanical Ventilation Information by Subject
- 4.2 Supplemental Oxygen Information by Subject

Figure Title

- 1.1.1 FiO₂ Observed Values by Treatment Group
- 1.1.2 FiO₂ Change from Baseline Values by Treatment Group
- 1.2.1 SpO₂ Observed Values by Treatment Group
- 1.2.2 SpO₂ Change from Baseline Values by Treatment Group
- 1.3.1 PCO₂ Observed Values by Treatment Group
- 1.3.2 PCO₂ Change from Baseline Values by Treatment Group
- 2.1 FiO₂ Change from Baseline Values by All Active and Control
- 2.2 SpO₂ Change from Baseline Values by All Active and Control
- 2.3 PCO₂ Change from Baseline Values by All Active and Control

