3.1.1 Primary Endpoints

The primary endpoints of this study will be derived from the safety evaluations, including adverse device effects (ADEs) reported from the time of randomization until 36 weeks PMA of upon discharge (Section 3.3).

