9 ADVERSE EVENT REPORTING

Information regarding the occurrence of AEs, including ADEs, will be assessed from the time of randomization until completion of Final Study Visit.

For purposes of this study, the following will be considered AEs of special interest if they occur within the primary observation period:

1. Bradycardia: defined as a heart rate < 100 bpm for ≥ 20 seconds
2. Desaturation: defined as $SpO_2 < 80\%$ for ≥ 20 seconds
3. A sustained apnea event defined as lasting ≥ 20 seconds and is coincident with at least one of the following: (1) HR < 100 bpm, (2) desaturation (oxygen saturation $< 80\%$), (3) requirement for intermittent positive pressure breaths using inflating pressures above the set CPAP pressure administered manually or mechanically through any patient interface.
4. Air leak, including pneumothorax and pneumomediastinum.

Complications related to placement of bi-nasal prongs as identified by the following:

- Bleeding
- Apparent obstruction of the nares
- Occlusion of the interface requiring removal and replacement
- Nasal irritation (erythema of nares or septum, inflammation of nares or septum)

All AEs must be followed by the PI until resolution or for at least 30 days post-study if the subject is stable.

Documentation of AEs in the eCRF must include the following parameters; (1) duration (time of onset and resolution), (2) severity or grade, (3) outcome, (4) action taken, and (5) relationship to study drug and/or device.

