6.4 ADVERSE EVENTS

All AEs will be coded by preferred term and system organ class (SOC) from the Medical Dictionary for Regulatory Activities (MedDRA), version 16.1 or above, and will be reviewed by the medical monitor or designee. All AEs will be summarized as categorical variables (frequency and percent) by treatment group unless otherwise indicated. AEs that are related to the device (ADEs) will be summarized with all AEs and separately. AEs will not be compared between treatment groups.

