6.4.3 Other AEs

AEs, other than those listed above, will be summarized by the MedDRA preferred term and SOC for all AEs, regardless of relationship to study drug, and for AEs at least remotely related. If an AE occurs multiple times for the same subject within the same term or body system, only the most severe occurrence for that term or body system will be counted.

In addition, all AEs will be summarized by severity (mild, moderate, severe), relationship to the study drug (unrelated, unlikely related, possibly related, definitely related), whether or not the AE was device related, gender, race, and ethnic origin.

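### The general AE tables report treatment-emergent events in dosed infants, while the endpoint is all AEs from randomization in all randomized infants

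*SAP*

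**What the plan says.** **Start of counting.** Protocol 3.1.1 takes the primary endpoints from the safety evaluations, "reported from the time of randomization until 36 weeks PMA" or discharge. Protocol Section 9 says that AEs "will be assessed from the time of randomization until completion of Final Study Visit". SAP 1.2.1 uses the same starting point for the primary objective.

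**Which events.** SAP 6.4 states: "All AEs will be summarized as categorical variables (frequency and percent) by treatment group unless otherwise indicated". SAP 6.4.3 says that AEs "will be summarized by the MedDRA preferred term and SOC for all AEs, regardless of relationship to study drug". Neither section applies a treatment-emergent filter.

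**Which infants.** The Protocol summary (Statistical Analysis), Protocol 13.1 and the SAP Executive Summary base the safety analysis on all randomized infants. SAP 6.1 instead defines the Safety Population as those given any study medication and applies it to every safety assessment.

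**The planned output.** In the SAP's List of Tables, Table 6.3.1 is "Treatment-Emergent Adverse Events by System Organ Class and Preferred Term – Safety Population". Tables 6.3.2 to 6.3.5 carry the same label and population. Tables 6.1, 6.2, 6.4.1, 6.5.1 and 6.6 (peri-dosing AEs, air leak, SAEs, device effects, deaths) lack the label but use the Safety Population. Neither document defines treatment-emergent for either arm.

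**The concern.** The primary objective is safety against nCPAP alone, in an open-label trial. The tables that deliver it therefore need one start time and one population for both arms, fixed before database lock. Here the text and the table titles disagree on both.

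The label matters because only the active arm has a dose. A programmer applying the usual first-dose convention would start active infants at aerosol and would have to choose something else for controls, most likely randomization. The missing interval falls in the acute early hours. The peri-dosing table cannot recover it, since that window opens when aerosol starts, and the planned AE listings cover only deaths and SAEs. On that convention, a non-serious bradycardia or desaturation before dosing in an active infant would appear in no AE table or listing, while the same event in a control would be counted.

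The population matters because the loss may be selective. The note in Protocol 4.3 requires entry criteria still to be met when therapy starts, so an infant who worsens after randomization may go undosed and then leaves every safety table.

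**Working it through.** **The plan's own figures.** 4 dosing groups × (8 active + 8 control) = 64 infants, 32 per arm, as stated. Randomization by 20 h plus aerosol within 2 h gives 22 h from birth, matching Protocol 2.3.1. There is no power calculation to reproduce (SAP 1.3 and 2.2.3).

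**1. Length of the possible clock gap (active arm).**
- Upper end: treatment begins within 2 h of randomization (Protocol 5.2.1).
- Lower end: PCO₂ monitoring starts after randomization and at least 30 minutes before aerosol (Protocol 7.1.5), so about 0.5 h.
- Share of the 48 h primary period: 0.5/48 = 1.0%; 2/48 = 4.2%.
- Share of the 72 h safety review window: 0.5/72 = 0.7%; 2/72 = 2.8%.
- Follow-up to 36 weeks PMA: longest, from 26w0d, 70 days × 24 = 1,680 h; shortest, from 28w6d and randomized at 20 h, 50 × 24 − 20 = 1,180 h. A 2 h gap is 2/1,680 = 0.12% to 2/1,180 = 0.17%.
- Total over the arm: at most 32 × 2 = 64 infant-hours. Controls counted from randomization lose 0.

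These figures assume that treatment-emergent means onset at or after first dose.

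**2. Effect of the Safety Population (independent of the label).**
- Each undosed active infant removes 1/8 = 12.5% of its dose group.
- Illustration for one group of 8: one infant has an AE before dosing and is not dosed, and one dosed infant has an AE. All randomized: 2/8 = 25.0%. Safety Population: 1/7 = 14.3%.
- Read literally, controls receive no study medication, so the set holds at most 32 active and 0 control infants. At least 32/64 = 50% of those randomized are lost.

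**3. How likely an undosed infant is.** Protocol 5.7 foresees infants randomized but not treated and gives no rate; SAP 3.3.1 assumes that everyone is dosed. For an assumed undosed rate p, the chance of at least one among n is 1 − (1 − p)^n:

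| Assumed p | At least 1 of 32 | At least 1 of 8 |
|---|---|---|
| 2% | 0.48 | 0.15 |
| 5% | 0.81 | 0.34 |
| 10% | 0.97 | 0.57 |

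**4. Number of AEs affected.** This cannot be computed: the documents give no AE rate.

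**The case against.** The best defence is that this is loose labelling. Every start time stated for AEs is randomization, and treatment-emergent appears only in table titles, so the titles could be read as meaning AEs after randomization. The arm-specific rule in SAP 9.1 defines baseline for measurements, not AE onset. The SAP plainly intends controls to appear: it plans a combined control group of 32, and SAP 6.5.4 gives controls their own time point. The safety committee sees all AEs (Protocol 6.1). Worsening and intubation are tabulated in the ITT population. There is no hypothesis testing, and SAP 6.4 says that AEs will not be compared between groups.

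Much of this stands, and it limits what can be claimed. A reader might infer any of the following, which the documents do not support:
- *The arms are counted from different clocks.* No passage says so; it follows only under an assumed convention.
- *The label removes undosed infants or controls.* SAP 6.1 does that. Deleting the label alone brings nobody back.
- *A definite count of AEs is lost.* At an assumed 3 to 10 AEs per infant in 48 h, spread evenly, the arithmetic gives 3 × 0.5/48 × 32 = 1 to 10 × 2/48 × 32 = 13 events over 32 infants. The rates are invented, and SAP 6.4.3 counts a repeated AE once per term or body system, so an infant with the same event later is still counted.
- *A pre-dose failure rate can be taken from the one-third to one-half of nCPAP infants said to deteriorate.* The protocol attaches no time frame to that figure.
- *The plan favours lucinactant.* That holds only if active infants start at dose and controls at randomization. If controls drop out altogether, there is no comparison to bias.

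The defence does not remove the contradiction. The objective is safety compared with nCPAP alone, the tables set the groups side by side, and the SAP leaves both the start of counting and the population open to more than one reading.

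**Conclusion.** The point holds as a conflict between the stated endpoint and the tables meant to report it. The endpoint is all AEs from randomization in all randomized infants; Tables 6.3.1 to 6.3.5 are titled with an undefined, narrower term on a dosed-only population. Two separate effects follow.

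- The label, on the first-dose convention and with controls counted from randomization (both assumptions), takes about 0.5 to 2 h from active infants only: 1.0% to 4.2% of the primary period and under 0.2% of full follow-up.
- The Safety Population definition drops undosed active infants at 12.5% of a dose group each and, read literally, excludes all controls. This is the larger defect and needs no assumption about the label.

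The expected numerical effect of the label is modest. In groups of 8, one undosed infant can visibly change a rate. The correction is worth making before database lock because it restores the protocol's own rule and removes an avoidable difference between arms.

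**What to change.** 1. Delete Treatment-Emergent from the titles of Tables 6.3.1 to 6.3.5. State in SAP 6.4 that AEs with onset at or after randomization are counted in both arms.
2. Revise SAP 6.1 so that the comparative safety tables (6.2, 6.3.1 to 6.3.5, 6.4.1, 6.6 and the other tables with a control column) include all randomized infants, controls included, with undosed active infants identified. Changing the 6.3 series alone would leave it on a different population from the air leak, SAE and mortality tables.
3. Keep the peri-dosing and device tables (5.1, 5.2, 6.1, 6.5.1) for dosed active infants. If an after-dose view of AEs is wanted, add it as an active-only table.
4. Correct SAP 3.3.1, which assumes that every subject is dosed.

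The cost is a short SAP amendment and retitled tables. AE onset times are already collected under Protocol Section 9, so no new data are needed. The small downside is that a few pre-dose AEs will appear in the active columns.
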